8.3 Diagnosis of PTS

PTS is a "syndrome" that produces a range of symptoms and clinical signs which differ in character and severity among patients (6). There is no "gold standard" criterion test to establish the diagnosis of PTS. In fact, correlations between "objective" findings on non-invasive tests and clinically important PTS disease have been poor-to-moderate (96,97). For example, valvular reflux is usually present on Duplex ultrasound in patients with PTS, but many patients with reflux do not have PTS symptoms, health impairment, or poorer QOL (26,96). As such, the diagnosis of PTS should not be based upon imaging or physiological findings alone. In clinical practice, PTS is diagnosed using clinical criteria (assessment of symptoms and clinical signs).

8.4 Justification of 24-Month Period for PTS Assessment

We adopted a 24-month follow-up period for assessment of PTS to ensure that we will not miss incident PTS cases due to insufficient duration of follow-up. As prospective studies have shown that 83-96% of PTS cases manifest by 2 years (2,3,5,31), we expect to miss very few cases. Two years also allows enough time for the more severe PTS manifestations to develop.

8.5 Selection of PTS Measures

A number of clinical scales have been developed to standardize the diagnosis of PTS and to rate its severity. Because there is no gold standard test for PTS, validation of PTS measures has relied upon showing that they correlate with important health outcomes such as quality of life, and with known anatomic/physiologic findings of chronic venous disease. In selecting the Villalta PTS Scale as our primary outcome measure, we placed high value upon its proven ability to identify subjects with clinically significant PTS after first-episode, proximal DVT. A detailed description of the evidence supporting Villalta PTS Scale is provided in **Appendix 7**. To enhance interpretation of the trial results, we will also use two additional measures which were designed to standardize the descriptive classification of chronic venous disease (CEAP Classification System) and to grade its severity (Venous Clinical Severity Score).

8.6 The Villalta PTS Scale

The Villalta PTS Scale (**Appendix 8**) rates the severity of 5 patient-reported symptoms (pain, cramps, heaviness, paresthesia, pruritus) and 6 clinician-observed signs (edema, skin induration, hyperpigmentation, pain during compression, venous ectasia, redness) of PTS on a 4-point scale (0=none, 1=mild, 2=moderate, 3=severe). The points are summed into a total score (range 0-33) for each leg (98). Subjects are categorized as having PTS if the total score in the leg with the index DVT is 5 or greater, or if an ulcer is present in that leg, at any time between the 6-month and the 24-month follow-up visits (see Section 6.2.8 and Section 15.2 for

circumstances in which PTS may be diagnosed before the 6-month follow-up visit in subjects who undergo unscheduled endovascular procedures). Subjects will also be categorized as having mild (score 5-9), moderate (score 10-14), or severe PTS (score >15 or leg ulcer).

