8 EFFICACY OUTCOMES

8.1 Primary Efficacy Outcome

Post-Thrombotic Syndrome (PTS) defined by the presence of a total score of 5 or greater on the Villalta PTS Scale in the leg with the index DVT, or an ulcer in that leg, that occurs at any time between the 6-month post-randomization follow-up visit and the 24-month visit (inclusive).

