PTS severity on Villalta PTS Scale: A difference as small as 1.25 units can be detected (5-point gradations define severity categories) (98, 111). Ultrasound outcomes: Assuming a 50% risk of deep venous reflux in the Control Arm and 10% inflation for losses due to withdrawal, death, or inadequate exams (rare), 142 subjects will provide 80% power to detect a 50% relative risk reduction for this outcome (alpha = 0.05, two-sided). 128 evaluable subjects will provide 80% power to detect effect sizes of 0.5 for reflux and obstruction on the continuous VSDS scales.

Regarding safety, we will perform a descriptive analysis of the rates of major bleeding and symptomatic PE in the two study Arms. These events are expected to occur infrequently (2% for major bleeding at 10 days and for symptomatic PE at 3 months) in the Control Arm. With 311 evaluable subjects per arm, if 2% of each group experiences an outcome, the 95% confidence interval on the difference of 0% will include an absolute decrease or increase of 2.4%.

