15.3.6 Severity of Post-Thrombotic Syndrome

Villalta severity classification (none, mild, moderate, severe) at 24 months will be compared between the two arms (4 x 2 table) using an exact Kruskal-Wallis nonparametric test with severity as a single ordered factor. In addition, ordinal logistic regression analysis adjusting for baseline factors will be performed. We will also use a linear mixed model for the repeated total Villalta scores (assessed at 10 days and 1, 6, 12, 18, and 24 months) with the baseline score serving as a covariate, to investigate their response patterns over time, and assess if they differ by treatment arm. In addition, the proportion of patients with either moderate or severe PTS will be compared between the two treatment groups using a stratum-adjusted Cochran-Mantel-Haenszel test. The CEAP Clinical Class and VCSS scores will be similarly analyzed.

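### As printed, the Villalta severity bands in protocol section 8.6 give a total score of exactly 15 without a leg ulcer no category

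*Protocol*

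**What the plan says.** Section 8.6 of the protocol builds the Villalta total from 5 symptoms and 6 signs, each rated "on a 4-point scale (0=none, 1=mild, 2=moderate, 3=severe". It then states: "The points are summed into a total score (range 0-33) for each leg (98". The severity bands follow: "mild (score 5-9), moderate (score 10-14), or severe PTS (score >15 or leg ulcer".

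Section 8.1 sets the primary outcome, "defined by the presence of a total score of 5 or greater on the Villalta PTS Scale", or an ulcer in the index leg. Section 15.1, in the remark on detectable differences for Villalta severity, notes that "5-point gradations define severity categories".

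The bands are used in section 15.3.6. There, "Villalta severity classification (none, mild, moderate, severe) at 24 months will be compared between the two arms (4 x 2 table") by an exact Kruskal-Wallis test, with an ordinal logistic regression in addition. The same section adds that "the proportion of patients with either moderate or severe PTS will be compared between the two treatment groups" by a stratum-adjusted Cochran-Mantel-Haenszel (CMH) test. Villalta severity at 6, 12, 18 and 24 months is a listed secondary efficacy outcome in section 8.2. No other section, and neither Villalta form in Appendix 8, gives numeric severity bands.

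**The concern.** The moderate band ends at 14 and the severe band, as printed, starts above 15. The value between them, 15, can occur. A subject with that total and no ulcer meets the definition of PTS but is neither mild, moderate nor severe.

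This is not detail that a protocol may leave to the statistical analysis plan. The protocol fixes the cut-points itself and fixes them with a hole, and it contradicts its own account of the width of the categories. At stake is how subjects at the moderate/severe boundary enter the categorical severity analyses. That boundary lies in the upper tail, where those analyses have the fewest subjects.

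**Working it through.** **1. Range of the score.** Inputs from 8.6: 11 items (5 + 6), each 0 to 3 in whole points. Minimum 0, maximum 11 × 3 = 33. This reproduces the stated range, and every whole number in it can occur.

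**2. Assigning all 34 scores to the bands as printed.**

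| Total, no ulcer | Band as printed |
|---|---|
| 0–4 | none |
| 5–9 | mild |
| 10–14 | moderate |
| 15 | no band |
| 16–33 | severe |

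Exactly one score has no band, and no score falls in two. With an ulcer, every score is severe, so the gap concerns 15 without an ulcer only. If severe includes 15, every score falls in exactly one band.

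**3. Against 15.1.** The bands 5–9 and 10–14 each span 5 points. Continuing in 5-point steps, the next band starts at 15, not 16.

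**4. Consequence in 15.3.6.** In the 4 × 2 table the subject has no row, and in the ordinal model no outcome level. In the moderate-or-severe proportion two literal readings are open: the subject is left out, or stays in the denominator as a non-event while a subject scoring 10 counts as an event. The protocol does not say which.

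**5. How many subjects.** The documents give no score distribution, so this step is an assumption. The implied SD from 15.1 is 1.25 / 0.25 = 5; SD 4 is added as an alternative. Evaluable subjects: 2 × 311 = 622. Take the total as negative binomial with mean m and p = m/SD², r = m²/(SD² − m):

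P(k) = Γ(k + r) / (k! Γ(r)) × p^r × (1 − p)^k, truncated to 0–33 and rescaled to sum to 1.

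Example, m = 4, SD = 5: p = 4/25 = 0.16 and r = 16/21 = 0.762, giving P(15) = 0.0078 and 622 × 0.0078 = 4.9.

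| SD | Mean | P(score ≥ 5) | P(15) | Expected of 622 |
|---|---|---|---|---|
| 4 | 3 | 23% | 0.46% | 2.9 |
| 4 | 4 | 34% | 0.59% | 3.7 |
| 5 | 3 | 22% | 0.57% | 3.6 |
| 5 | 4 | 31% | 0.78% | 4.9 |
| 5 | 5 | 42% | 1.03% | 6.4 |
| 5 | 6 | 53% | 1.36% | 8.4 |

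The third column is the check on plausibility. Section 15.1 expects 30% cumulative PTS over 24 months in controls and a one-third reduction with the experimental treatment, so the proportion at or above 5 at a single visit should be about 30% or lower. Means of 3 to 4 give 22% to 34%, roughly in line. Means of 5 and 6 do not fit. The usable range is therefore 0.5% to 0.8%, or 3 to 5 subjects over both arms, about 6% to 7% of those scoring 10 or more.

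**The case against.** **The symbol may be a reading artefact.** The point rests on one character, and an underlined greater-than sign can lose its underline when a PDF is read by program. The text at hand shows signs of this. Section 9.3 gives a repeat-ultrasound window as 7 plus 2 days where 9.2 has plus-or-minus. Section 8.13 has reflux above 0.5 seconds where Appendix 12 has at or above 0.5 seconds, although that could be a drafting slip. On the other side, the greater-than-or-equal sign survives in the Villalta threshold of 15.2 and in the thrombus-extension criterion of 9.3. An artefact is possible but not shown. This part of the objection stands: it lowers confidence and makes checking the source the first step.

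**The intended meaning can be inferred.** The 5-point gradations point to 15 as the start of severe, and section 15.6 requires an analysis plan approved before unblinding, so a clarification would probably be made blind. This also stands, and it limits the severity. It does not repair section 8.6, which is the only place with numeric bands.

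**Stronger readings that the documents do not support.** A reader might infer that subjects scoring 15 drop out of both severity analyses. That is the direct reading for the table, but only one of two for the proportion. A reader might also infer that the primary result is affected. It is not: the primary definition is 5 or greater, or an ulcer. Finally, a reader might put the number affected as high as 8 of 622. That needs a mean score of 6, at which 53% would have PTS at a single visit, against the plan's 30% cumulative.

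**Conclusion.** The point holds as a wrong cut-point in the printed text: a total of 15 without an ulcer is PTS with no severity grade, and 8.6 conflicts with 15.1. It touches the categorical severity analyses of 15.3.6, which are secondary and tested at 0.01 under section 15.3. The primary outcome, the sample size and the mixed model on total Villalta scores are untouched.

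The size is small, about 3 to 5 of 622 subjects over both arms. That rests on an assumed negative binomial with mean 3 to 4 and SD 4 to 5. It slightly overstates the gap, because anyone scoring 15 with an ulcer is still graded severe. Severity is minor. Confidence is moderate, because the printed symbol has not been checked against the source.

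**What to change.** Check the symbol in section 8.6 of the source document. If it already reads greater than or equal to 15, nothing needs changing. If it is a strict greater-than sign, define the severe band as a score of 15 or greater, or leg ulcer, so that the PTS bands are 5–9, 10–14 and 15–33 or ulcer. Use these bands for the table, the ordinal model and the moderate-or-severe comparison in 15.3.6.

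The cost is one symbol and the matching derivation code, with no effect on data collection or sample size. Made before unblinding, the change leaves no choice about these subjects to be made after results are known.

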8.7 Clinical-Etiologic-Anatomic-Pathologic (CEAP) Classification System

All subjects will have their Basic CEAP Clinical Class assessed for each limb (99,100). The limb will be categorized into one of 8 descriptive "Clinical Classes" based upon the dominant physical exam findings observed (101) (see **Appendix 9**):

- C0 = no disease
- C1 = telangiectasias or reticular veins
- C2 = varicose veins
- C3 = edema
- C4a = pigmentation or eczema
- C4b = lipodermatosclerosis or atrophie blanche
- C5 = healed venous ulcer
- C6 = active venous ulcer

Subjects will be assigned the highest Class for which they have a component sign, and will be classified as symptomatic (S) or asymptomatic (A). The ascending severity of the Clinical Classes has been shown to correlate with QOL (102,103). In ATTRACT, the Etiologic ("E"), Anatomic ("A") and Pathophysiologic ("P") components of the CEAP System will not be used.

8.8 Venous Clinical Severity Score (VCSS)

The VCSS is a 30-point venous severity scoring system (104-107). Its components were derived from selected elements of CEAP (eight clinical signs and one symptom of chronic venous disease) that exhibit change over time. Extra weight was given to signs from the more severe (C4–C6) CEAP classes (**Appendix 10**). Use of the VCSS should improve our ability to distinguish subjects with different severities of PTS and to assess PCDT's cost-effectiveness.

8.9 Administration of PTS Measures

The Villalta PTS Scale will be administered to subjects at baseline and at the 10-day and the 1, 6, 12, 18, and 24-month follow-up visits. CEAP and VCSS will be administered to subjects at the 6, 12, 18 and 24-month follow-up visits. Prior to initial use, examining clinicians will complete training and certification on their proper administration to ensure uniform administration across all Clinical Centers. The examiners must be blinded to the subjects' treatment allocation.

The day before follow-up visits, subjects should receive a telephone reminder to not wear compression stockings on the day of the visit, and to not reveal to clinic staff which therapy they received (PCDT or no PCDT) and which leg was affected with the DVT. Subjects should be examined in the afternoon (the later the better) to allow the symptoms and signs of PTS to

manifest. At the time of assessment, the following procedures should be followed:

- The subject should be asked to rate (absent, mild, moderate, severe) the 5 symptoms on the Villalta PTS scale for each leg, record his/her ratings on the Villalta PTS Symptoms Form, and also complete the QOL Questionnaire (see below) and Leg Pain Severity Form.
- 2. The subject should be brought to a well-lit examining room. The subject's legs should be unclothed and he/she should be seated facing the blinded clinician (nurse or physician).
- 3. Subsequently, and without access to the subject's rating of symptoms, the blinded clinician should assess the clinical signs required for Villalta, CEAP, and VCSS measures; measure the leg circumference; and record these results on the respective Case Report Forms.
- 4. The blinded clinician should check that all scales have been filled out correctly and completely before the subject leaves. If there are missing items, the blinded clinician should ask the subject (without coercion) if he/she would like to complete the form.

Measurement scales will be available in English and Spanish. If subjects have difficulty completing forms (e.g., language barrier, visual impairment, literacy), blinded study personnel or a translator should assist, taking care to avoid influencing the subject's responses.

8.10 Health-Related Quality of Life (QOL)

We will assess general and venous disease-specific QOL at baseline and at the 1-month, 6-month, 12-month, 18-month and 24-month follow-up visits.

8.10.1 General QOL

General QOL will be measured using the Short-Form Health Survey-36, Version 2 (SF-36v2), a validated, widely-used gold standard instrument (108). The SF-36 has been used in other DVT studies to complement measures of PTS and venous disease-specific QOL (10,12,102,109). The SF-36v2 will be available for use in both English and Spanish versions.

8.10.2 Venous Disease-Specific QOL

Venous disease-specific QOL will be measured using the VEINES-QOL/Sym measure, a patient self-assessment questionnaire (110). The instrument consists of 25 question items that measure venous symptoms, limitations in daily activities due to venous disease, psychological impact of venous disease, and change over the past year. Responses are rated on 2-point to 7- point Likert scales of intensity, frequency, or agreement. The VEINES-QOL/Sym has undergone comprehensive and rigorous psychometric evaluation and is acceptable, reliable, valid, and responsive for use as a patient-reported measure of outcome in studies of chronic venous

disease, including PTS and DVT (109-111). The VEINES-QOL/Sym measure will be available in the originally validated English version and in a certified Spanish translation.

8.10.3 Administration of QOL Instruments

The SF-36 and VEINES-QOL/Sym will be combined into a single questionnaire that takes 15-20 minutes for an average patient to complete (**Appendix 11**). Following a standard orientation, the subject will complete the questionnaire in a quiet office. The study nurse will then check for missing data and politely (without coercion) encourage the subject to respond to all items. The nurse administering the questionnaire must be blinded to the subject's treatment allocation.

8.10.4 Scoring of QOL Instruments

QOL data will be scored by blinded DCC personnel using established computer algorithms which include imputation of missing data (112,113). Summary scores will be computed for the SF-36 Physical (PCS) and Mental (MCS) Component Scales, and for the VEINES-QOL (impact of venous disease upon QOL) and VEINES-Sym (symptom severity) summary scales.

8.11 Resolution of Leg Pain and Swelling

To determine if PCDT leads to faster DVT symptom resolution, the severity of pain in each leg will be assessed on a 7-point Likert scale at baseline and 10-day and 1-month follow-up. The subject will be asked to "Please rate the overall intensity of "pain" or "discomfort" that you have felt in your leg during the past 24 hours by checking one response on the following scale" (1 = No pain, 2 = Very mild pain, 3 = Mild pain, 4 = Moderate pain, 5 = Severe pain, 6 = Very severe pain, 7 = Extremely severe pain). Likert scales are widely validated for pain severity assessment (114,115). The Likert scale and accompanying instructions will be available in the originally validated English version and in a certified Spanish translation. Calf circumference 10cm below the tibial tuberosity will also be measured at baseline and 10-day and 1-month follow-up. At these visits, venous symptoms and signs will also be assessed using the Villalta PTS Scale. The clinician performing these assessments must be blinded to subject treatment allocation.

8.12 Venographic Thrombus Extent (Experimental Arm Only)

Two sets of venograms will be analyzed in each Experimental Arm subject: (a) the baseline venogram of the proximal veins (popliteal vein through infrarenal IVC) obtained after initial catheter insertion into the venous system and before PCDT; and (b) the final venogram of the proximal veins obtained after PCDT and any adjunctive procedures, and before sheath removal. The primary goal of the venogram evaluation is to determine the degree of thrombus elimination and correlate it with the likelihood of developing PTS. The venograms will be transmitted to the DCC and initially evaluated for overall quality in standardized fashion by blinded Independent

Adjudication Committee physicians who are experienced with venogram adjudication in DVT trials. Feedback to Clinical Centers will be provided when inadequate exams are identified in order to encourage better quality venography in subsequent subjects. Readers will quantify clot burden using the components of the Marder score that describe the proximal veins (116).

8.13 Ultrasound Substudy - Valvular Reflux and Residual Thrombus

A 1-year follow-up venous Duplex ultrasound of the index leg will be performed in a consecutive 142-subject subgroup in 7 Clinical Centers. The primary goal of the Ultrasound Substudy will be to determine if prevention of valvular reflux and/or venous obstruction from residual thrombus represents a primary mechanism underlying any effect of PCDT upon the cumulative incidence and severity of PTS. We will assess: (a) the presence of valvular reflux (flow reversal for > 0.5seconds after standardized distal compression with an automatic cuff inflator) in the common femoral, deep femoral, femoral, popliteal, great saphenous, and small saphenous veins (117,118); and (b) the presence of residual thrombus (assessed in the leg veins mainly by incomplete compressibility) in the iliac, common femoral, deep femoral, femoral, popliteal, and great saphenous veins (77). Reflux will be evaluated with subjects standing and bearing weight on the contralateral limb (see Appendix 12 for recommended ultrasound exam protocol). The exams must be performed in standardized fashion by Clinical Center sonographers blinded to treatment allocation, recorded in real time on super VHS videotapes or digital media, and transmitted to the Ultrasound Core Laboratory. Blinded Core Lab personnel will analyze the exams for overall quality, interpret findings, record them on an Ultrasound Case Report Form (CRF), and transmit it to the DCC. At the DCC, reflux and obstruction will be quantified from the CRFs by blinded personnel using the Venous Segmental Disease Score (VSDS) in which values assigned to the presence of reflux and obstruction in specific lower extremity veins are summed to yield a Reflux Score and an Obstruction Score (102,106,107).

9 SAFETY OUTCOMES

The following safety outcomes will be assessed for each subject over the 24-month period.

- Major bleeding and minor bleeding
- Need for transfusion
- Intracranial bleeding
- Symptomatic pulmonary embolism
- Symptomatic recurrent venous thromboembolism
- Mortality

9.1 Bleeding

Evaluation of clinically overt bleeding will depend upon the suspected bleeding site. For example, subjects with suspected intracranial bleeding will undergo a head CT scan and subjects with suspected retroperitoneal bleeding will undergo a CT scan of the abdomen/pelvis. Clinically overt bleeding will be classified as "Major" if it is associated with a fall in the hemoglobin level of at least 2.0 g/dl, transfusion of \geq 2 units of red blood cells, or involvement of a critical site (e.g. intracranial, intraspinal) (119). Less severe clinically overt bleeding will be classified as minor. To distinguish clinically important hemorrhage from hemoglobinuria (which is routinely observed in subjects undergoing mechanical thrombectomy), discoloration of the urine during or after mechanical thrombectomy will not by itself be considered to indicate the presence of clinically-overt bleeding. Major bleeding, minor bleeding, need for transfusion, and intracranial bleeding will be assessed during the study period and reported. To aid in evaluating the relationship of bleeding events to rt-PA administration, they will also be categorized by whether they occurred within 3 days after the initiation of PCDT. Data on complications will be captured on the Case Report Forms in a way that enables their outcomes to be categorized according to FDA guidelines and SIR reporting standards (48,120).

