 (1) via injection through the vascular sheath or a multisidehole catheter; (2) in Technique A patients only, via the Trellis as described in Appendix 4, Steps 4-8; or (3) in Technique B patients only, via the Angiojet (PowerPulse or Rapid Lysis method) as described in Appendix 5, Step 4.
- 3. Perform a repeat venogram. If significant residual obstructing thrombus is present, position a multisidehole infusion catheter within the thrombus and perform Infusion CDT (rt-PA at 0.01 mg/kg/hr, maximum dose 1.0 mg/hr) as outlined in **Appendix 6**. (For Technique C subjects, this will simply represent a continuation of the initial rt-PA infusion.) The rt-PA infusion should continue until near-complete (> 90%) thrombolysis is observed, clinically-overt bleeding becomes evident, or until a maximum of 24 hours (for Technique A or Technique B) or 30 hours total (for Technique C) of rt-PA infusion has occurred.
- 4. The steps in Section 7.3.5 may be repeated as needed, but the above limits on rt-PA dose, infusion duration, device activation time, and AngioJet infusate volume must be followed.

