11.1 Scheduled Visit 1 – Follow-Up Assessment at 10 Days

At 10 days ± 3 days after randomization, subjects:

51

- rate their leg pain (7-point Likert scale) (both legs)
- have their leg circumference measured (both legs)
- undergo assessment using the Villalta PTS Scale (both legs)
- are provided sized-to-fit elastic compression stockings (ECS)
- have their platelet count obtained to assess for heparin-induced thrombocytopenia (HIT)
- have adverse events, thrombotic and bleeding events, hospitalizations, physician visits, anticoagulant regimen, and their cost diary reviewed and recorded
- are re-assessed for removal of a retrievable IVC filter (if one is present)

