12.6 Equal Surveillance of Both Treatment Arms

As subjects in both treatment Arms will receive the same standard DVT therapy and follow-up, the intensity of surveillance will not differ between them.

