Appendix 6: Protocol for Infusion-First PCDT (Technique C)

- 1. Review the initial venogram and estimate the length of the clotted venous segment. Advance a multisidehole catheter into position with its sideholes spanning the thrombus.
- 2. Obtain the following rt-PA solution from the pharmacy: 10mg rt-PA in 10 ml Sterile Water for Injection, USP, diluted to a total volume of 1000 ml in 0.9% normal saline (rt-PA concentration 0.01 mg/ml). Infuse through the multisidehole catheter at a rate of 50-100 ml/hr (corresponding to 0.01 mg/kg/hr, with maximum allowable dose 1.0 mg/hr). For patients in whom fluid volume is of concern or in whom an ultrasound infusion catheter is selected, the physician may concentrate the rt-PA solution to 0.02 mg/ml 0.04 mg/ml (10mg rt-PA in 250-500 ml total volume, infused at 12.5 50 ml/hr). If more than one venous access site is used, the rt-PA dose may be split per physician discretion. The physician may also utilize the vascular sheath (with or without added sideholes) to infuse part of the rt-PA. All infusion catheters should be used per their Instructions for Use (package insert).
- 3. During infusion CDT, the patient should be placed at bedrest and the affected leg should be elevated. Mechanical compression adjuncts may be used per the physician's standard practice. If UFH is used, it should be infused at subtherapeutic levels (6-12 units/kg/hr, maximum allowable dose 1000 units/hr) through the vascular sheath (preferably) or through a peripheral IV (if the sheath is being used to infuse rt-PA), to a target PTT of less than 2 times control. The patient should be monitored in an ICU or stepdown unit and peripheral blood taken at least every 12 hours for hemoglobin, partial thromboplastin time (PTT), and platelet count. A fibrinogen level may be obtained if this is the physician's standard practice.
- The rt-PA infusion may be halted temporarily or permanently at physician discretion if there is evidence of bleeding (see Section 7.3.4), the PTT > 100 seconds, or the fibrinogen level < 100 mg/dl. When rt-PA is stopped, saline should be infused to maintain catheter patency.
- After 6-24 hours, the patient should return to the procedure suite. At each return visit, follow the procedures described in Section 7.3.5. In particular, the use of rheolytic thrombectomy is encouraged at the first follow-up visit to speed thrombolysis (see Appendix 5, Steps 5-9).

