Appendix 14: Study Procedures and Assessments

PROCEDURE	Pre Rand Screening	Pre Rand Baseline	Rand	Initial Tmt	Visit 1 10 days ±3 days	Visit 2 30 days ±7 days	Visit 3 6 mo ±1 mo	Visit 4 12 mo ±1 mo	Visit 5 18 mo ±1 mo	Visit 6 24 mo ±2 mo
Informed Consent	Х									
History & Physical	Х									
Blood Tests	X ⁽¹⁾				X ⁽²⁾					
Start AC in both arms	Х	Х		Х						
Rate Leg Pain ⁽³⁾		Х			Х	Х				
Measure Leg Circumference (3)		Х			Х	Х				
QOL Questionnaire (SF-36, VEINES)		Х				Х	Х	Х	Х	Х
Duplex Ultrasound		Х				Х		X ⁽⁴⁾		
Randomization			R							
PCDT/venograms - PCDT arm only				X ⁽⁵⁾						
Dispense ECS					Х					
Record/report on-serious AEs					Х	Х				
Record/report serious AEs					Х	Х	Х	Х	Х	Х
Review AC, ECS, Cost Diary					Х	Х	Х	Х	Х	Х
Villalta PTS Scale (3)		Х			Х	Х	Х	Х	Х	X
VCSS Scale ⁽³⁾							Х	Х	Х	Х
CEAP Clinical Class ⁽³⁾							Х	Х	Х	Х

⁽¹⁾ CBC with platelets, PT/INR, creatinine; a pregnancy test will be obtained only in women of childbearing potential.

(2) Platelet count to assess for HIT

 $^{(3)}$ Assess both legs. NOTE: For bilateral DVT, designate the "index leg" prior to randomization.

⁽⁴⁾ The 12-month follow-up Duplex ultrasound will be obtained only in Ultrasound Substudy patients.

⁽⁵⁾ Venograms performed immediately before and after PCDT will be obtained only in the Experimental (PCDT) arm patients.

Abbreviations: QOL quality of life; AE adverse event; ECS elastic compression stockings; AC anticoagulation; PCDT pharmacomechanical catheter-directed intrathrombus thrombolysis.

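### The hemoglobin-fall criterion for major bleeding is measured on a schedule only during rt-PA infusion, so major-versus-minor grading of overt bleeds may differ by arm

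*Protocol*

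**What the plan says.** Protocol Section 9.1 grades only bleeding that is clinically overt. Such a bleed is major if it is "associated with a fall in the hemoglobin level of at least 2.0 g/dl", if at least 2 units of red cells are transfused, or if a critical site is involved. Everything else overt falls into the lower grade: "Less severe clinically overt bleeding will be classified as minor". The section ties the work-up to the suspected bleeding site and gives CT scans as examples. It does not ask for a hemoglobin, and it does not say which earlier value the fall is measured from.

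The scheduled blood tests are set out elsewhere:

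- **Screening, both arms.** Appendix 14 lists "CBC with platelets, PT/INR, creatinine".
- **During rt-PA infusion.** Appendix 6, step 3, requires "peripheral blood taken at least every 12 hours for hemoglobin, partial thromboplastin time (PTT), and platelet count". Section 7.3.5 brings in patients who started with Technique A or B and still have obstructing thrombus, for whom the physician is to "position a multisidehole infusion catheter within the thrombus and perform Infusion CDT" as that appendix describes.
- **Controls.** Section 7.2 allows outpatient care and schedules INR draws at least every third day while heparin continues.
- **Day 10, both arms.** Section 11.1 and Appendix 14 ask for a platelet count only.

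Section 12.6 reasons that both arms get the same standard therapy and follow-up, and concludes that "the intensity of surveillance will not differ between them". Section 15.3.2 compares major bleeding over the first 10 days and makes a similar comparison for any bleeding.

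**The concern.** A fall in hemoglobin can be established only where a second value exists. One of the three routes to a major bleed therefore depends on a test that is scheduled for some patients and left to clinical choice for the rest. Only the PCDT arm is scheduled for infusion, so the difference in sampling becomes a difference between arms, and it falls inside the 10-day window that is formally compared.

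The adjudicators are blinded (Section 9.5), but blinding cannot supply a value that was never drawn. At stake is the comparison of a key harm with any benefit on PTS. Section 15.5 names major bleeding among the outcomes the monitoring board is particularly to review. An error in one direction, however small, is not removed by sample size or blinding.

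**Working it through.** **1. Who has a hemoglobin scheduled after screening**

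| Group | Acute phase | Day 10 |
|---|---|---|
| Control | INR only (7.2) | platelets |
| PCDT, single session, no infusion | none in Appendix 4 or 5; INR as in controls (7.3.7) | platelets |
| PCDT with infusion (Technique C, or A/B going on to infusion) | at least every 12 hours, for up to 30 h (C) or 24 h (A/B) | platelets |

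The divide is infusion versus no infusion. It becomes a divide between arms because the control arm has no scheduled infusion.

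**2. The plan's own safety figure**

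Section 15.1 gives 2% per arm, 311 evaluable per arm, and a 95% interval of plus or minus 2.4 points.

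- Wald: 1.96 × √(2 × 0.02 × 0.98 / 311) = 2.20 points.
- Agresti-Caffo: 2.35 points. Newcombe with 6/311 in each arm: 2.45 points.

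The last two agree with the stated 2.4, so the figure is reproduced.

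**3. How large the distortion could be**

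The protocol supplies only the 2% rate. The other inputs are assumptions:

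- h = share of true major bleeds that qualify by hemoglobin alone;
- u = share of those that go unmeasured when no test is scheduled;
- f = share of such bleeds in the PCDT arm that occur under scheduled sampling (controls: f = 0).

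With equal true rates in both arms, observed rate = 2% × [1 − h × u × (1 − f)].

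| h | u | Control | PCDT, f = 1 | PCDT, f = 0.5 | Spurious difference, points (f = 1 / f = 0.5) | Ratio (f = 1 / f = 0.5) |
|---|---|---|---|---|---|---|
| 0.25 | 0.5 | 1.75% | 2.0% | 1.875% | 0.25 / 0.125 | 1.14 / 1.07 |
| 0.5 | 0.5 | 1.5% | 2.0% | 1.75% | 0.5 / 0.25 | 1.33 / 1.17 |
| 0.5 | 1 | 1.0% | 2.0% | 1.5% | 1.0 / 0.5 | 2.0 / 1.5 |

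Example, second row: control 2% × (1 − 0.25) = 1.5%; PCDT at f = 0.5 is 2% × (1 − 0.125) = 1.75%. In events, a difference of 1.0 point is 0.01 × 346 = 3.5 per arm, and 0.125 point is 0.4.

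The column f = 1 is an upper bound. It needs every hemoglobin-only bleed in the PCDT arm to fall under scheduled sampling, although single-session patients have none and infusion lasts at most 24 to 30 hours of a 10-day window.

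**4. Chance of a false signal**

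Section 15.3 sets 0.01 two-sided for secondary tests. With 346 per arm, equal true rates of 2% and f = 1, the chance of a significant result against PCDT is about 1%, 2%, 7% and 21% when h × u is 10%, 25%, 50% and 75%. This is a normal approximation and rough at such small counts. The rows of step 3 have h × u of 12.5%, 25% and 50%.

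**The case against.** The strongest case against is that the gap is narrow and partly covered already. Several stronger readings are tempting, and the documents do not support them.

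- **That serial hemoglobin creates major bleeds, or upgrades minor ones automatically, for instance through hydration or hemolysis.** Section 9.1 first requires overt bleeding, requires the fall to be associated with it, and says urine discoloration after thrombectomy is not by itself overt bleeding. Two blinded adjudicators apply a manual that is not at hand. Sampling can only help move an overt bleed from minor to major.
- **That no hemoglobin exists in controls.** Unscheduled is not unmeasured. A clinician may well order one for an overt bleed on anticoagulants, and Section 13.5 asks for relevant source documents with the Suspected Bleeding form for bleeds after 30 days. The unmeasured share is unknown.
- **That the bias is a ratio of 1.33 or 2.0.** Those figures rest on assumed shares and on full capture across the whole PCDT arm.
- **That major bleeding is the designated main safety outcome.** The protocol lists it first but ranks none.
- **That Section 12.6 is simply false.** Read with its opening clause, it can be taken to cover the follow-up visits, which are identical. As worded, it still claims more than holds for laboratory monitoring.

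Two further points stand. The any-bleeding comparison in Section 15.3.2 cannot be distorted by major-versus-minor grading, and transfusion and intracranial bleeding are reported separately. Tabulating events by criterion is ordinary detail for the statistical analysis plan promised in Section 15.6, so its absence from the protocol is no fault.

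None of this removes the core: the criterion and the schedule do not match, and the mismatch runs along treatment lines.

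**Conclusion.** The concern holds in a limited form. For overt bleeds that could qualify by hemoglobin alone, the grade may depend on whether the patient was on infusion, and hence on arm. The likely direction is against PCDT, assuming that unscheduled hemoglobin is drawn less often than scheduled hemoglobin.

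The protocol does not allow the size to be derived. Under the assumptions shown, the spurious difference lies between 0.125 and 1.0 points, all below the protocol's 2.4-point half-width. A false significant result is therefore possible but not likely. The reason to act is that the error is systematic and cheap to guard against, and that Section 12.6 currently rules it out.

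**What to change.** 1. **Analysis (Section 15.3.2 or the statistical analysis plan).** Tabulate major bleeds by qualifying criterion: hemoglobin fall only, transfusion, critical site. Repeat the 10-day comparison without the hemoglobin-only events, and read it alongside the any-bleeding comparison.
2. **Measurement.** Record hemoglobin from the day-10 blood sample already drawn in both arms. On the Suspected Bleeding form, record whether hemoglobin was measured, the value nearest the bleed, and the reference value, identically in both arms. Asking for the value nearest the bleed matters because a form may be completed well after the event.
3. **Wording.** Amend Section 12.6 to say that scheduled follow-up is the same in both arms but laboratory monitoring during infusion is not.

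The cost is a small addition to the case report form and one extra table, with no extra visit or needle at day 10. A few more control bleeds may be classed as major. The day-10 value is only a supplement, because it can miss an earlier transient fall. None of these steps changes a dose or a treatment rule.
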